5.2.5.2 Bone densitometry

Bone densitometry will be performed at the times indicated in the [Flow Chart](#) according to standard institutional practice and bone mineral density will be recorded. In the event that bone mineral density changes by >5% from baseline, bone densitometry will be repeated at least two months after the change is first observed to determine whether the change has persisted and constitutes a DLT.

In addition to the above, the SMC will regularly review any reported bone mineral density changes of >5% from baseline which have not yet been confirmed after two months and if necessary, appropriate action will be agreed upon.

5.2.5.3 Testing for Cytokine Release

Patients must remain under observation for potential signs and symptoms of cytokine release for at least 6 hours following the end of infusion of BI 905681. If no signs or symptoms are observed during the first three administrations the duration of observation may be reduced to 3 hours for subsequent administrations. For patients who require systemic steroids around the time of administration of BI 905681 or during the post-treatment monitoring period, hospitalisation and monitoring for at least 24 hours is mandatory.

Clinical signs and symptoms of cytokine release will be recorded as AEs. In addition, a panel of cytokines (including, but not limited to IL-2, IL-6, IL-10, IFN- γ , TNF- α , MCP-1) will be measured in peripheral blood in order to monitor release of cytokines after BI 905681 administration. Cytokine measurements will be performed in conjunction with each infusion

at the time points specified in [Appendix 10.2](#).

In addition to the scheduled cytokine measurements, ferritin will be measured at baseline (Cycle 1 Day 1). If a clinically manifested CRS occurs at any time point, unscheduled blood sampling for cytokine and ferritin measurement will be performed, ideally at the start of symptoms (and before start of corticosteroid treatment) and 48-72 hours after the start of symptoms.

Cytokines and ferritin will be measured in a central lab authorised by Boehringer Ingelheim using immunoassay techniques, such as BD Cytometric Bead Array (CBA) and MSD assay. Details are specified in [Appendix 10.2](#), and in the Laboratory Manual.

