7.3.5 Pharmacokinetic and pharmacodynamic analyses

Refer to [Appendix 10.1](#) for pharmacokinetic parameters to be calculated using non-compartmental analysis (NCA). The derivation of pharmacokinetic parameters is described in detail in the current BI and [REDACTED] SOPs.

All patients in the treated set who received at least one dose of BI 905681 and provided at least one valid serum concentration value will be included in the pharmacokinetic analysis. Patients who are considered as not evaluable will be listed with their individual serum concentrations and individual pharmacokinetic parameters, however, they will not be included in descriptive statistics for serum concentrations, pharmacokinetic parameters or other statistical assessment.

Every effort will be made to include all concentration data in an analysis. If not possible, a case to case decision is required whether the value should only be excluded from half-life estimation or the complete analysis.

If a concentration is only excluded from half-life determination, it will be used for all other calculations (e.g. descriptive statistics) and for graphical presentation. If a concentration value is excluded from all calculations, it will not be presented graphically or used for the calculation of descriptive statistics and parameter determination. However the excluded concentration itself will be listed in the clinical trial report associated with an appropriate flag.

Concentrations will be used for graphs and calculations in the format that is reported in the bioanalytical report. Noncompartmental pharmacokinetic analyses of the serum concentration-time data will be performed using a validated software program, e.g. Phoenix WinNonlin Version 5.2. Only concentrations within the validated concentration range will be used for the calculation of pharmacokinetic parameters. For pre-dose samples, the actual sampling time will be set to zero.

Serum concentrations will be plotted graphically versus time for all evaluable patients as

listed in the drug serum concentration-time tables. For the presentation of the mean profiles, the geometric and arithmetic mean and the planned blood sampling times will be used. If the actual sampling time deviates significantly from the planned time, the corresponding serum concentration will be excluded from the calculation of descriptive statistics.

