10. APPENDICES

10.1 PHARMACOKINETIC ANALYSES

If data allow and if scientifically reasonable, the following pharmacokinetic parameters of BI 905681 will be evaluated using non compartmental analysis methods according to the current internal BI and [REDACTED] SOPs.

After the first doses (before steady state is achieved):

- C_{max} (maximum measured serum concentration of BI 905681 in serum).
- [REDACTED]
- AUC_{0-tz} (area under the serum concentration-time curve of the analyte over the time interval from 0 up to the last quantifiable data point).

[REDACTED]

If deemed necessary, further appropriate pharmacokinetic parameters might be calculated.

Blood sampling time points for PK, ADA, cytokines and ferritin are given in [Appendix 10.2](#).

10.2 TIME SCHEDULE FOR PHARMACOKINETIC (PK), ADA AND CYTOKINE BLOOD SAMPLING AND ECG ASSESSMENT

Table 10.2: 1

Time schedule for PK, ADA and cytokine blood sampling and ECG assessment in Schedule A

Cycle	Day	Time Point (hh:min)	CRF Time / planned time	PK BI 905681	ADA	Cytokines	ECG	Tumour Biopsy
		Any time before 1 st infusion						X
1 and 2	1	Before start of BI 905681 infusion	-0:05	X	X	X ^a	X ^b	
		Start of BI 905681 infusion	0:00					
		End of infusion	1:00 ^c				X ^{d,e}	
		Immediately after end of infusion ^e	1:00 ^c	X ^f		X ^f		
		0.5h after the end of infusion (± 5 min)	1:30 ^c	X				
		3h after the end of infusion (± 10 min)	4:00 ^c	X		X		
		7h after the end of infusion (± 15 min)	8:00 ^c	X		X		
	2	24h after start of infusion (± 1 hr)	24:00	X		X		X ^g
	4	48:00-96:00	72:00	X				
	8	144:00-192:00	168:00	X			X ^d	
	15	288:00-384:00	336:00	X				
3 and 4	1	Before start of BI 905681 infusion	-0:05	X	X	X	X ^b	
		Start of BI 905681 infusion	0:00					
		End of infusion	1:00 ^c				X ^e	
		Immediately after end of infusion ^f	1:00 ^c	X ^f		X ^f		
		3h after the end of infusion (± 10 min)	4:00 ^c			X		
		7h after the end of infusion (± 15 min)	8:00 ^c			O		
		24h after start of infusion (± 1 hr)	24:00			X		
	2	144:00-192:00	168:00	X				
	8	288:00-384:00	336:00	X				
Cycle 5 onwards	1	Before start of BI 905681 infusion	-0:05	X	X	X	X ^b	
		Start of BI 905681 infusion	0:00					
EOT	N/A	N/A	N/A	X	X		X	
FU	N/A	N/A	N/A	X	X			

O = Optional. To be taken if the patient is already in the clinic.

a A sample for ferritin testing will be collected before the start of infusion on cycle 1 Day 1.

b Pre-dose ECG will be performed within 10 minutes prior to start of infusion.

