c The planned times assume an infusion duration of 60 min. If the infusion duration is shorter or longer, the

Proprietary confidential information © 2019 Boehringer Ingelheim International GmbH or one or more of its affiliated companies

PK and cytokine sample times for the end of infusion sample and all subsequent Day 1 samples should be adjusted accordingly (timings calculated from the end of infusion, as indicated in the column 'Time Point') and the actual times recorded in the eCRF.

- d Only required in Cycle 1
- e End of infusion ECG will be performed within 10 minutes prior to the end of infusion
- f PK sample must be taken within 5 min after the end of infusion. Cytokine sample must be taken within 30 min after the end of infusion.
- g Only required in Cycle 2. The on-treatment biopsy time point may be adapted based on PK analysis.

Proprietary confidential information © 2019 Boehringer Ingelheim International GmbH or one or more of its affiliated companies

Table 10.2: 2 Time schedule for PK, ADA and cytokine blood sampling and ECG assessment in Schedule B

Cycle	Day	Time Point (hh:min)	CRF Time / planned time	PK BI 905681	ADA	Cytokines	ECG	Tumour Biopsy
		Any time before 1 st infusion						X
1 and 2	1	Before start of BI 905681 infusion	-0:05	X	X	X ^a	X ^b	
		Start of BI 905681 infusion	0:00					
		End of infusion	1:00 ^c					X ^{d, e}
		Immediately after end of infusion ^e	1:00 ^c	X ^f		X ^f		
		0.5h after the end of infusion (±5 min)	1:30 ^c	X				
		3h after the end of infusion (±10 min)	4:00 ^c	X		X		
		7h after the end of infusion (±15 min)	8:00 ^c	X		X		
	2	24h after start of infusion (±1 hr)	24:00	X		X		X ^h
	4	48:00-96:00	72:00	X				
	8	144:00-192:00	168:00	X				X ^d
	15	Before start of BI 905681 infusion	335:55	X	X	X	X ^{b,d}	
		Start of BI 905681 infusion	336:00					
		End of infusion	337:00 ^c					
		Immediately after end of infusion ^e	337:00 ^c	X ^f		X ^f		
		3h after the end of infusion (±10 min)	340:00 ^c			X		
		7h after the end of infusion (±15 min)	344:00 ^c			X		
		24h after start of infusion (±1 hr)	360:00	X		X		
	22	480:00-528:00	504:00	X				

Proprietary confidential information © 2019 Boehringer Ingelheim International GmbH or one or more of its affiliated companies

Table 10.2: 2 (cont.) Time schedule for PK, ADA and cytokine blood sampling and ECG assessment in Schedule B

Cycle	Day	Time Point (hh:min)	CRF Time / planned time	PK BI 905681	ADA	Cytokines	ECG	Tumour Biopsy

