3 and 4	1	Before start of BI 905681 infusion	-0:05	X	X	X	X ^b	
		Start of BI 905681 infusion	0:00					
		End of infusion	1:00 ^c				X ^e	
		Immediately after end of infusion ^e	1:00 ^c	X ^f		X ^f		
		3h after the end of infusion (±10 min)	4:00 ^c			X		
		7h after the end of infusion (±15 min)	8:00 ^c			O		
	2	24h after start of infusion (±1 hr)	24:00			O		
	8	144:00-192:00	168:00	X				
	15	Before start of BI 905681 infusion	335:55	X		X		
		Start of BI 905681 infusion	336:00					
		End of infusion	337:00 ^c					
		Immediately after end of infusion ^e	337:00 ^c			X ^f		
		3h after the end of infusion (±10 min)	340:00 ^c			X		
		7h after the end of infusion (±15 min)	344:00 ^c			O		
	16	24h after start of infusion (±1 hr)	360:00			O		
	22	480:00-528:00	504:00	X				
Cycle 5 onwards	1	Before start of BI 905681 infusion	-0:05	X	X	X	X ^b	
		Start of BI 905681 infusion	0:00					
		Before start of BI 905681 infusion	335:55	X ^g		X		
EOT	N/A	N/A	N/A	X	X		X	
FU	N/A	N/A	N/A	X	X			

O = Optional. To be taken if the patient is already in the clinic.

a A sample for ferritin testing will be collected before the start of infusion on cycle 1 Day 1.

b Pre-dose ECG will be performed within 10 minutes prior to start of infusion.

c The planned times assume an infusion duration of 60 min. If the infusion duration is shorter or longer, the PK sample times for the end of infusion sample and all subsequent Day 1 samples should be adjusted accordingly (timings calculated from the end of infusion, as indicated in the column 'Time Point') and the actual times recorded in the eCRF.

d Only required in Cycle 1

e End of infusion ECG will be performed within 10 minutes prior to the end of infusion

f PK sample must be taken within 5 min after the end of infusion. Cytokine sample must be taken within 30 min after the end of infusion.

g Only required in Cycles 5 and 6

h Only required in Cycle 2

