## **6.7 BASELINE, TIME WINDOWS AND CALCULATED VISITS**

### **Visit labels**

Study days and visits will be labelled according to the CTP's flow chart. The visit schedule with accompanying details can also be found in the flow charts in the CTP.

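### Appendix 10.2 requires 24-hour PK and cytokine samples in Cycles 1 and 2, but both flow charts limit the whole Day 2 visit to Cycle 2, so a site scheduling by the flow chart has no visit for them after the first infusion

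*Protocol*

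**What the plan says.** **Appendix 10.2.** Section 5.2.5.3 states that "Cytokine measurements will be performed in conjunction with each infusion", "at the time points specified in" Appendix 10.2. In Table 10.2:1 (Schedule A) the block for Cycles 1 and 2 has a Day 2 row ("24h after start of infusion (± 1 hr") with an unrestricted mark for PK and another for cytokines. The biopsy mark on that row carries footnote g: "Only required in Cycle 2. The on-treatment biopsy time point may be adapted based on PK analysis". Table 10.2:2 (Schedule B) has the same Day 2 row ("24h after start of infusion (±1 hr"), and again only the biopsy is limited: "h Only required in Cycle 2".

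**Flow charts.** In both, the dagger stands on the Day 2 column heading and restricts the column to Cycle 2. The column holds the biopsy, PK and cytokine marks, with a window of ±1 day. Day 4, by contrast, is marked for Cycles 1 and 2. Footnotes l and m refer to Appendix 10.2 for the detailed cytokine and PK schedules.

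**Which source governs.** Section 6.1 has patients attend at the flow-chart time points. Section 5.3.2 cites the flow charts and Tables 10.2:1 and 10.2:2 together for PK. No rule says which prevails if they differ.

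**The concern.** The two schedules disagree about whether blood is drawn 24 hours after the first dose. The appendix footnotes suggest that the authors meant to hold back only the biopsy until Cycle 2, while the flow-chart dagger holds back the whole visit.

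Schedule A Cycle 1 is the first human exposure and the DLT evaluation period. The protocol monitors closely for cytokine release: patients within a cohort are treated at least 72 hours apart, there are CRS stopping rules, and Section 5.2.6.1 notes that symptoms can appear hours or days after dosing. A scheduled cytokine measurement at 24 hours belongs to that monitoring. The first administration is also the one from which the secondary PK endpoints, Cmax and AUC0-tz, are calculated.

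**Working it through.** **1. Day 2 entries side by side**

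| Item | Appendix 10.2 (both schedules) | Flow charts (both schedules) |
|---|---|---|
| 24 h PK | Cycles 1 and 2 | Cycle 2 only |
| 24 h cytokines | Cycles 1 and 2 | Cycle 2 only |
| Biopsy | Cycle 2 only | Cycle 2 only |
| Window | ±1 h | ±1 day |

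The sources agree on the biopsy and disagree on both blood samples.

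**2. Does another Cycle 1 visit cover the time?** The appendix window is 24 ± 1 h, that is 23 to 25 h after the start of infusion. Routine observation lasts 6 h after the end of a 1 h infusion, to about 7 h. The last planned Day 1 sample is at 8:00. The next visit, Day 4, is 48 to 96 h after dosing. Nothing overlaps 23 to 25 h.

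**3. What is lost in Schedule A Cycle 1 (Table 10.2:1)**
- Cytokines: pre-dose, end of infusion, 3 h, 7 h and 24 h make 5. Without 24 h, 4 remain, the last at 8:00. The next scheduled sample is pre-dose in Cycle 2.
- PK: pre-dose, end of infusion, 0.5 h, 3 h, 7 h, 24 h, Day 4, Day 8 and Day 15 make 9. Without 24 h, 8 remain. The gap runs from 8:00 to the planned 72:00, which is 64 h (40 to 88 h across the Day 4 window).

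**4. Effect on AUC.** The protocol gives predicted values at 1.0 mg/kg of Cmax 21.8 µg/mL and AUC0-168h 1,900 µg·h/mL, but no half-life. Assumptions: these two values describe a first-dose two-compartment profile after a 1 h infusion; terminal half-life 8 to 16 days; distribution half-life 4 to 48 h; samples at planned times.

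With the linear trapezoidal rule, omitting 24 h changes the AUC by

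Δ = 64(C8 + C72)/2 − [16(C8 + C24)/2 + 48(C24 + C72)/2] = 24·C8 + 8·C72 − 32·C24.

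- Near the upper end (terminal 16 days, distribution 6 h): C8 = 16.511, C24 = 12.685, C72 = 11.040 µg/mL. Δ = 396.3 + 88.3 − 405.9 = 78.7 µg·h/mL. The exact AUC0-336h of this profile is 3,245, so the shift is 78.7/3,245 = 2.4 percentage points.
- Near the lower end (terminal 8 days, distribution 48 h, log trapezoidal rule, where a segment contributes Δt·(C1 − C2)/ln(C1/C2)): C8 = 20.292, C24 = 17.314, C72 = 11.246. The single 8 to 72 h segment gives 980.9; the two segments give 300.2 + 675.0 = 975.2. Δ = 5.7, and 5.7/2,546 = 0.2 percentage points.

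Over such profiles, both trapezoidal rules and AUC to 336 or 504 h, the shift is about 0.1 to 2.5 percentage points, always upward.

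**5. Cmax.** In these profiles the peak is at the end of infusion. That sample and the 0.5 h sample are Day 1 samples and are not touched.

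**The case against.** The strongest reply is that the documents already lead the reader to the right table. Section 5.2.5.3 names Appendix 10.2 as the source of the cytokine time points, and the Day 2 PK and cytokine cells carry footnotes that point there. A careful site would find the Cycle 1 requirement. This has force: sites need not have missed the sample, and divided practice between sites is a possibility, not something the documents show. But the footnotes supply detail and do not lift the dagger, and Section 6.1 tells sites to schedule by the flow chart. A coordinator who books from it has no Cycle 1 Day 2 visit to which the detail could attach.

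A reader might draw stronger conclusions that the documents do not support:

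- *That the secondary PK endpoints are compromised.* Cmax is essentially untouched, the AUC shift is small, and both endpoints are summarised descriptively.
- *That samples taken within ±1 day would be discarded.* Section 7.3.5 says "If the actual sampling time deviates significantly from the planned time, the corresponding serum concentration will be excluded" from descriptive statistics. The ±1 day window belongs to the flow-chart Day 2, which does not exist in Cycle 1, and the sentence does not remove a concentration from the AUC calculation.
- *That the SAP would lose the sample.* SAP Section 6.7 ("Study days and visits will be labelled according to" the flow chart) governs labels and drops no data. Mean PK profiles use planned sampling times.
- *That no late cytokine data could exist.* Clinically manifest CRS triggers unscheduled sampling, ideally at symptom onset and again 48 to 72 h later. What is lost is the scheduled sample in patients without manifest CRS.
- *That the pre-dose-only cytokine sampling from Cycle 5 is a further error.* It meets the appendix schedule; wanting a post-dose partner is a preference.

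**Conclusion.** The inconsistency stands, and it decides what is collected after the first dose. For Schedule A Cycle 1 the cost of following the flow chart is 1 of 5 cytokine samples, the only scheduled post-dose one after 8 h, and 1 of 9 PK samples. The cytokine loss is the more important. The AUC0-tz effect of about 0.1 to 2.5 percentage points rests on the assumed half-lives and on the protocol's predicted exposure, not on observed data.

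These counts, and the description as first human exposure, apply to Schedule A. Schedule B has the same Day 2 contradiction, but its Cycle 1 has further cytokine samples around the Day 15 infusion, and the SAP records that only Schedule A was investigated.

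Two neighbouring mismatches belong with this one. Table 10.2:2 requires PK and cytokine samples at 360:00, 24 h after the start of the Day 15 infusion, in Cycles 1 and 2, and the Schedule B flow chart has no column for them. Table 10.2:1 marks a 24 h cytokine sample as required in Cycles 3 and 4, where the flow chart has no Day 2 visit; Schedule B marks the corresponding sample optional. Which status was intended for Schedule A cannot be told from the documents.

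This should be corrected, but it does not threaten the primary analysis.

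**What to change.** Reconcile the flow charts with Appendix 10.2 in one amendment:

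1. In both flow charts, move the Cycle 2 restriction from the Day 2 column heading to the tumour-biopsy cell.
2. Mark the Day 2 PK and cytokine cells for Cycles 1 and 2, and give these blood samples the appendix window of ±1 h.
3. In the Schedule B flow chart, provide for the 360:00 PK and cytokine samples in Cycles 1 and 2, or change Table 10.2:2 if they are not intended.
4. State whether the 24 h cytokine sample in Schedule A Cycles 3 and 4 is required or optional, and align the flow chart accordingly.

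The cost is mainly table and footnote wording. Steps 1 and 2 add no sample beyond those the appendix already requires; the burden is one short visit per patient in Cycle 1. Since the SAP reports early termination, the useful step for data already collected is to state, by dose cohort, how many treated patients have the Cycle 1 24 h PK and cytokine samples.

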5.2.5.4 Ophthalmologic Assessment

Ophthalmologic assessment will be performed for all patients at Screening. This will require a visit to the ophthalmologist. The following assessments will be performed;

- Best corrected visual acuity (BCVA): BCVA will be determined using the early treatment diabetic retinopathy study (ETDRS) visual acuity chart starting at a test distance of 4 meters. The BCVA score is the number of letters read correctly by the patient. The assessment will be performed by a trained person under standard conditions regarding examination room and equipment.
- Colour fundus photography: Seven-field or modified 4-field digital fundus photographs will be obtained from both eyes by a qualified person.
- Spectral domain optical coherence tomography (SD-OCT): The retinal layers and thickness can be visualized and measured by SD-OCT. The assessment will be performed by a qualified person, and only Heidelberg, Zeiss or Topcon equipment will be used.

The same ophthalmologic assessments will be repeated within 48-72 hours if the patient develops visual symptoms during the trial. If the ophthalmological assessments are repeated, they should be performed using the same devices/equipment as used at Screening. Additionally, a full retinal examination must be performed. Treatment with BI 905681 will be withheld until this ophthalmologic assessment confirms it is safe to restart BI 905681.

5.2.6 Assessment of adverse events

5.2.6.1 Definitions of AEs

Adverse event

An adverse event (AE) is defined as any untoward medical occurrence in a patient or clinical investigation subject administered a medicinal product and which does not necessarily have to have a causal relationship with this treatment.

An AE can therefore be any unfavourable and unintended sign (including an abnormal laboratory finding), symptom, or disease temporally associated with the use of a medicinal product, whether or not considered related to the medicinal product.

The following should also be recorded as an AE in the CRF and BI SAE form (if applicable):

- Worsening of pre-existing conditions (for the underlying disease adhere to chapter “Exemptions to SAE reporting” in [Section 5.2.6.2](#))
- Changes in vital signs, ECG, physical examination, laboratory test results and other safety parameters included in [Section 5.2.5](#), if they are judged clinically relevant by the investigator.

If such abnormalities already exist prior to trial inclusion they will be considered as baseline conditions and should be collected in the eCRF.

Serious adverse event

A serious adverse event (SAE) is defined as any AE which fulfils at least one of the following criteria:

- results in death,
- is life-threatening, which refers to an event in which the patient was at risk of death at the time of the event; it does not refer to an event that hypothetically might have caused death if more severe.
- requires inpatient hospitalisation or
- requires prolongation of existing hospitalisation,
- results in persistent or significant disability or incapacity, or
- is a congenital anomaly / birth defect,
- is deemed serious for any other reason if it is an important medical event when based on appropriate medical judgement which may jeopardise the patient and may require medical or surgical intervention to prevent one of the other outcomes listed in the above definitions. Examples of such events are intensive treatment in an emergency room or at home for allergic bronchospasm, blood dyscrasias or convulsions that do not result in hospitalisation or development of dependency or abuse.

AEs considered “Always Serious”

In accordance with the European Medicines Agency initiative on Important Medical Events, Boehringer Ingelheim has set up a list of AEs, which by their nature, can always be considered to be “serious” even though they may not have met the criteria of an SAE as defined above. A copy of the latest list of “Always Serious AEs” will be provided upon request. These events should always be reported as SAEs as described in [Section 5.2.6.2](#).

Every new occurrence of cancer of new histology must be classified as a serious event regardless of the duration between discontinuation of the trial medication and must be

reported as described in [Section 5.2.6.2](#), subsections “AE Collection” and “AE reporting to sponsor and timelines”.

Adverse events of special interest (AESIs)

The term AESI relates to any specific AE that has been identified at the project level as being of particular concern for prospective safety monitoring and safety assessment within this trial, e.g., the potential for AEs based on knowledge from other compounds in the same class.

AESIs need to be reported to the [REDACTED] within the same timeframe that applies to SAEs, please see ‘AE reporting to sponsor and timelines.’

For this trial, the following events will be considered as AESIs:

Hepatic injury

A hepatic injury is defined by the following alterations of hepatic laboratory parameters: For patients with normal liver function at baseline (ALT, AST and bilirubin within normal limits at baseline)

- an elevation of AST and/or ALT ≥ 3 times ULN combined with an elevation of total bilirubin ≥ 2 times ULN measured in the same blood draw sample, and/or
- aminotransferase (ALT, and/or AST) elevations ≥ 10 times ULN

For patients with abnormal liver function at baseline (AST and/or ALT $>$ ULN)

- an elevation of AST and/or ALT ≥ 5 times ULN combined with an elevation of total bilirubin ≥ 2 times ULN measured in the same blood draw sample, and/or
- Marked peak aminotransferase (ALT, and/or AST) elevations ≥ 10 times ULN

These lab findings constitute a hepatic injury alert and the patients showing these lab abnormalities need to be followed up according to the “Potential DILI checklist” provided in the ISF.

In case of clinical symptoms of hepatic injury (icterus, unexplained encephalopathy, unexplained coagulopathy, right upper quadrant abdominal pain, etc.) without lab results (i.e., ALT, AST, total bilirubin) available, the Investigator should make sure these parameters are analysed, if necessary in an unscheduled blood test. Should the results meet the criteria of hepatic injury alert, the procedures described in the Potential DILI checklist should be followed.

Dose Limiting Toxicity

Any medical event fulfilling the criteria of DLT (see [Section 4.1.7](#)) should be reported as an AESI.

Infusion-related Reactions (including Cytokine Release Syndrome)

The following terms describe those events that are to be considered infusion-related reactions. Regardless of grade, these events, when occurring within 72 hours of study drug administration, are considered AESIs and must be reported as such;

- Allergic reaction

Proprietary confidential information © 2019 Boehringer Ingelheim International GmbH or one or more of its affiliated companies

- Anaphylaxis
- Cytokine-release syndrome
- Serum sickness
- Infusion reactions
- Infusion-like reactions
- Any other event which the investigator determines may be a potential infusion-related AE
- Treatment of infusion-related reactions and the handling of subsequent trial dosing are described in [Section 4.1.6.2](#).

The initial clinical sign of a CRS is fever that can rise to high temperatures and is often associated with flu-like symptoms (e.g. nausea, fatigue, headache, myalgias, malaise, chills, rigor, tremor, hypoxia, tachypnea, rash, vomiting, diarrhoea, abdominal pain, muscle and joint pain, and generalised weakness). CRS symptoms may occur quickly during or after administration, or after several hours or days. Patients will be assessed for signs and symptoms of CRS and CRS will be reported as an AESI.

Management guidelines and treatment of CRS are described in [Section 4.1.6.3](#).

Retinal toxicity

Any retinal toxicity (Standardised MedDRA Query ‘Retinal Disorder’) will be reported as an AESI.

Other AESIs

Based on safety observations during the trial, the SMC may define additional AEs as AESIs. If this occurs, investigators will be informed in writing.

Severity of AEs

The severity of AEs should be classified and recorded in the CRF according to the CTCAE v5.0.

Causal relationship of AEs

Medical judgement should be used to determine the relationship, considering all relevant factors, including pattern of reaction, temporal relationship, de-challenge or re-challenge, confounding factors such as concomitant medication, concomitant diseases and relevant history.

Arguments that may suggest that there is a reasonable possibility of a causal relationship could be:

- The event is consistent with the known pharmacology of the drug.
- The event is known to be caused by or attributed to the drug class.
- A plausible time to onset of the event relative to the time of drug exposure.
- Evidence that the event is reproducible when the drug is re-introduced
- No medically sound alternative aetiologies that could explain the event (e.g., pre-existing or concomitant diseases, or co-medications)

- The event is typically drug-related and infrequent in the general population not exposed to drugs (e.g. Stevens-Johnson syndrome).
- An indication of dose-response (i.e. greater effect size if the dose is increased, smaller effect size if dose is diminished).

Arguments that may suggest that there is no reasonable possibility of a causal relationship could be:

- No plausible time to onset of the event relative to the time of drug exposure is evident (e.g., pre-treatment cases; diagnosis of cancer or chronic disease within days / weeks of drug administration; an allergic reaction weeks after discontinuation of the drug concerned)
- Continuation of the event despite the withdrawal of the medication, taking into account the pharmacological properties of the compound (e.g., after 5 half-lives). Of note, this criterion may not be applicable to events whose time course is prolonged despite removing the original trigger.
- Additional arguments amongst those stated before, like alternative explanation (e.g., situations where other drugs or underlying diseases appear to provide a more likely explanation for the observed event than the drug concerned).
- Disappearance of the event even though the trial drug treatment continues or remains unchanged.

